7.4. Continuation of Treatment Beyond Radiographic Progression

In the event of radiographic progression per RECIST v1.1 but in the absence of clinical deterioration, worsening ECOG performance status, or disease progression that may compromise organ function, the subject may continue to receive study treatment with ivosidenib, nivolumab, and/or ipilimumab at the discretion of the treating physician in consultation with the Sponsor. Nivolumab will be permitted for up to a maximum of 24 months from date of first dose. If there is clinical deterioration or continued radiographic progression documented on subsequent imaging, treatment with either ivosidenib, nivolumab, or both will be discontinued, and the subject will complete the EOT and Safety Follow-up visits and enter Survival Follow-up.

All other elements of the main consent including description of reasonably foreseeable risks or discomforts, or other alternative treatment options, will still apply. Treatment beyond progression may be administered during or after localized interventions (surgery/radiation therapy).

8. ASSESSMENT OF SAFETY

All AEs and other situations relevant to the safety of the participants must be followed up and fully and precisely documented to ensure that the Sponsor has the necessary information to continuously assess the benefit-risk balance of the clinical trial.

8.1. Specification of Safety Parameters

Safety measurements, including a limited physical examination and vital signs including weight, performed during the study are indicated in [Table \(4.1.2\) 1](#).

8.2. Methods and Measurement Times

Safety measurements will include ECOG performance status, ECG, and clinical laboratory assessments (hematology, chemistry, thyroid function tests, coagulation, and pregnancy testing) and be performed locally per the schedule outlined in [Table \(4.1.2\) 1](#).

Clinical laboratory assessment details for assessments performed centrally are described in the study lab manual.

8.3. Definition of Adverse Events

An AE is defined as any untoward medical occurrence in a subject participating in a clinical study, whether or not there is a causal relationship with the IMP and/or experimental procedures, occurring or detected from the date the participant signs the information and consent form, irrespective of the period of the study (periods without administration of the IMP (e.g., run-in period) are also concerned).

An AE can therefore be:

- Any unfavorable and unintended sign (including an abnormal finding from an additional examination such as lab tests, X-rays, and ECG) that is deemed clinically relevant by the Investigator.
- Any symptom or disease.
- Any worsening during the study of a symptom or a disease already present when the participant entered the study (increase in frequency and/or intensity).

Fatal studied disease progression, detected during a study visit or at an additional examination or occurred since the previous study visit. An AE can arise from any use of the drug (e.g., off-label use, use in combination with another drug) and from any route of administration, formulation, or dose, including an overdose.

Of note:

- Any hospitalization for administration of anti-tumoral treatment and/or associated protocol (during or after the study) or other care measures for cancer (e.g., overnight hospital stay to receive a blood or platelets transfusion), for social reasons, educational purpose (e.g., learning of diabetes management by the participant) or routine check-up should not be considered as an AE and should not be reported in the eCRF.
- Any clinically significant abnormal laboratory findings or other abnormal safety assessments, which are associated with the studied disease should not be considered as an AE unless judged by the Investigator to be more severe than expected for the participant's condition.
- Non-fatal studied disease progression should not be considered as an AE.
- The following procedures, whether planned before the study or not, whether leading to a hospitalization or not, **should not be reported in the eCRF and should be kept in the source data (or participant file):**
 - therapeutic procedures related to a non-aggravated medical history (e.g., cataract extraction not due to an aggravation of the cataract during the study, haemodialysis sessions related to a renal insufficiency not aggravated during the study),
 - prophylactic procedures (e.g., sterilization, wisdom teeth removal),
 - comfort procedures (e.g., cosmetic surgery),
 - control procedures of a pre-existing condition without aggravation (e.g., colonoscopy to control the remission of colon cancer).

8.4. Definition of Serious Adverse Events

An SAE is any AE that, at any dose:

- results in death,
- is life-threatening⁽¹⁾,
- requires insubject hospitalization or prolongation of existing hospitalization,
- is medically significant⁽²⁾,
- results in persistent or significant disability/incapacity⁽³⁾,
- is a congenital anomaly/birth defect⁽⁴⁾.

⁽¹⁾ Life-threatening in this context refers to an event in which the participant was at risk of death at the time of the event; it does not refer to an event which hypothetically might have caused death if it were more severe.

⁽²⁾ Any event that might not be immediately life-threatening or result in death or hospitalization, but might jeopardize the participant or might require intervention to prevent one of these outcomes (for example: oedema or allergic bronchospasm that required intensive treatment at home, blood dyscrasias, convulsions that do not result in hospitalization, or development of drug dependence or drug abuse). The Investigator should exercise his/her scientific and medical judgement to decide whether or not such an event requires expedited reporting to Sponsor.

⁽³⁾ Disability/incapacity in this context refers to any event that seriously disrupts the ability of the participant to lead a normal life, in other words leads to a persistent or permanent significant change, deterioration, injury or perturbation of the participant's body functions or structure, physical activity and/or quality of life.

⁽⁴⁾ Congenital anomaly or birth defect refers to the exposure to the IMP before conception (in men or women) or during pregnancy that resulted in an adverse outcome in the child.

It is under Investigator's responsibility to evaluate the AE seriousness according to international guidance (see [ICH Topic E2A](#) and [EU DIRECTIVE 2001/20/EC of 4 April 2001](#) or further [regulation \(EU\) No 536/2014](#)). The Sponsor will review the AE seriousness. The seriousness may be upgraded (but never downgraded).

8.5. Definition of Overdose

This refers to any intake of a quantity of IMP that is above the maximum dose recommended in the study protocol, independent of the occurrence of any AE.

The quantity should be considered per administration or cumulatively regarding the maximum dose recommended in the study protocol.

8.5.1. Overdose or Incorrect Administration

Study treatment overdose is the accidental or intentional use of the drug in an amount higher than the dose being studied. An overdose or incorrect administration of study treatment is not an AE unless it results in untoward medical effects. Any study treatment overdose or incorrect administration of study treatment should be noted on the Study Drug Administration eCRF.

All AEs associated with an overdose or incorrect administration of study treatment should be recorded on the Adverse Event eCRF. If the associated AE fulfills serious criteria, the event should be reported to the Sponsor by the Investigator within 24 hours after learning of the event.

8.6. Definition of Adverse Event of Special Interest

An adverse event of special interest (AESI) is one of scientific and medical interest or concern regarding the IMP for which recording rules, special documentation such as hospital records and/or adjudication committee could be appropriate. It may be a serious or non-serious AE that may require further investigation in order to be characterized and understood.

8.6.1. QT Prolongation

Any QT prolongation event assessed as Grade ≥ 2 (*i.e.*, QTcF interval longer than 480 msec or ≥ 60 msec change from baseline with Torsade de pointes or polymorphic ventricular tachycardia or signs/symptoms of serious arrhythmia), irrespective of the seriousness, should be reported as an AESI to the Sponsor within 24 hours. See Section 8.6.1.1 for further details on managing subjects with QT prolongation. Heart rate-corrected QT interval will be calculated using Fridericia's formula (QTcF = QT/RR^{1/3}).

8.6.1.1. Management of QT Prolongation

Events of QT prolongation (*i.e.*, QTcF Grade ≥ 3) should be reported as AESIs to the Sponsor within 24 hours, according to expedited reporting procedures (see Section 8.3).

Subjects may be at increased risk for the development of QT prolongation when treated with ivosidenib in combination with fluoroquinolones, azole antifungal agents, or serotonin (5-HT3) antagonists. Investigators must be vigilant; refrain from administering concomitant medications associated with QT prolongation and if no other therapeutic options are available, monitor subjects receiving study treatment with the combination of these drugs and evaluate ECG and electrolytes (including potassium, magnesium, and calcium), particularly in subjects presenting with nausea, vomiting, or diarrhea. Systemic administration of a moderate or strong CYP3A4 inhibitor requires careful monitoring of QTcF.

Subjects who experience QT prolongation (*i.e.*, QTcF > 480 msec; NCI CTCAE Grade ≥ 2) while receiving study treatment should be promptly evaluated for causality of the QT prolongation and managed according to the following guidelines.

- Levels of electrolytes (potassium, calcium, and magnesium) should be checked, and supplementation given to correct any values outside the normal range.
- Concomitant therapies should be reviewed and adjusted as appropriate for medications with known QT prolonging effects.
- If no other cause is identified and the Investigator believes it is appropriate, particularly if QTcF remains elevated (after the above measures have been implemented, or as determined by the Investigator), study treatment may be interrupted, and an ECG should be rechecked in approximately 1 week after the QT prolongation event was first observed or more frequently as clinically indicated.

Please refer to [Table \(8.12.1\) 1](#) for the management of QT prolongation by NCI CTACE grade.

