6.1. IMPs Administered

Product Description and Dosage Form	Concentration	Primary Packaging	Secondary Packaging
Ivosidenib / tablet	Tablets of 250 mg	One pillbox = 60 tablets of 250 mg	One box containing one pillbox of 60 tablets
Nivolumab / solution for injection	CC1 mg/mL	One vial = CCI mL CC1 mg/mL	One box containing one vial
Ipilimumab / solution for injection	CC1 mg/mL	One vial = CCI mL vial at CC1 mg/mL	One box containing one vial

It is recommended that each dose should be taken with or without food. Subjects taking ivosidenib with food should be advised to avoid grapefruit or grapefruit products and avoid

consuming a high-fat meal (Please refer to examples of low-fat and high-fat meals in [Appendix 12](#)).

For treatment dose modifications due to toxicities, please refer to Section [8.12](#). All the IMP tracking is managed in RTSM in real time. The procedures to be followed by the Investigator or authorized person are detailed in the training video embedded in RSTM or user manual.

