8.12. Dose Modification and Management for Adverse Events

8.12.1. Study Treatment Dose Modification and Management Associated with Ivosidenib

For any AE, including AEs not specifically mentioned in [Table \(8.12.1\) 1](#), the Investigator may decide to delay dosing or modify the dose of ivosidenib based on clinical judgment. These decisions should be discussed with the Sponsor prior to implementation. Dose modifications of ivosidenib from 500 mg to 250 mg will be permitted on study for management of AEs ([Table \(8.12.1\) 1](#)). If more than one AE occurs that would require a dose modification, upon resolution of all AEs to baseline or Grade 1, ivosidenib should be dose reduced to 250 mg. Re-escalation may be allowed with approval from the Sponsor.

Dose delays are discouraged, except as needed for management of AEs. Dose delays up to 28 days will be permitted at the discretion of the Investigator in consultation with the Sponsor for reasons including management of AEs and for mitigating circumstances (e.g., planned procedures). Palliative biliary decompression procedures will be permitted on study and will not require interruption of ivosidenib (see Section 8.12.5).

If the subject cannot resume ivosidenib within 28 days, the subject should be discontinued from ivosidenib. Other reasons for treatment termination are provided in Section 5.4.1. If ivosidenib is discontinued, the subject may continue receiving nivolumab and ipilimumab or nivolumab alone. If subject permanently discontinues treatment from all three drugs, the EOT and Safety Follow-up visits will be completed as well as the PFS follow-up (if disease has not progressed) and Survival Follow-up visits. Exemptions may be considered for those subjects who are determined by the Investigator to have received clinical benefit from treatment. If a dose is delayed for the management of an AE, the subject should resume the study at the next planned visit within a dosing cycle.

If a strong CYP3A4 inhibitor must be co-administered, reduce the ivosidenib dose to 250 mg QD. If the strong inhibitor is discontinued, increase the ivosidenib dose (after at least 5 half-lives of the strong CYP3A4 inhibitor) to the recommended dose of 500 mg QD.

Table (8.12.1) 1 - Management of Ivosidenib related QT Prolongation and Adverse Events by NCI CTCAE Grade

NCI CTCAE Grade	Management

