Grade 2: Average QTc interval greater than 480 msec up to 500 msec	
 Monitor and supplement electrolyte levels as clinically indicated. Review and adjust concomitant medications with known QTc interval-prolonging effects. Interrupt ivosidenib. Restart ivosidenib at 500 mg once daily after the QTc interval returns to less than or equal to 480 msec. Monitor ECGs should be conducted at least weekly for 2 weeks following resolution of QTc prolongation.
Grade 2 nausea or vomiting (related or unrelated)	
 Consider holding dose of ivosidenib until resolution of adverse event (AE) to Grade ≤ 1 within 28 days of supportive therapy. Manage with supportive therapy according to the institutional standard of care. May resume ivosidenib at same dose.
Grade 3: Average QTc interval greater than 500 msec	
 Monitor and supplement electrolyte levels as clinically indicated. Review and adjust concomitant medications with known QTc interval-prolonging effects. Interrupt ivosidenib. Resume ivosidenib at a reduced dose of 250 mg once daily when QTc interval returns to within 30 msec of baseline or less than or equal to 480 msec. Monitor ECGs at least weekly for 2 weeks following resolution of QTc prolongation. Consider re-escalating the dose of ivosidenib to 500 mg daily if an alternative etiology for QTc prolongation can be identified.

NCI CTCAE Grade	Management
Grade 3 AEs (related, first event)	
 Interrupt ivosidenib until toxicity resolves to Grade 1 or lower, or baseline, then resume at 250 mg, or re-escalation to 500 mg with Sponsor approval. If Grade 3 toxicity recurs (a second time), interrupt ivosidenib dose until the toxicity resolves, then resume 250 mg daily. If Grade 3 toxicity recurs (a third time), discontinue ivosidenib.
Grade 4 AEs (related) including QTc interval prolongation with signs/symptoms of life-threatening arrhythmia	
 Discontinue ivosidenib permanently.

Abbreviations ECG = electrocardiogram; NCI CTCAE = National Cancer Institute Common Terminology Criteria for Adverse Events; QTc = heart rate-corrected QT interval; QTcF = heart rate-corrected QT interval using Fridericia's method.

Note Per NCI CTCAE, version 4.03.

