8.12.3. Dose Modification for Ivosidenib, Nivolumab and Ipilimumab

When study interventions are administered in combination, attribution of an AE to a single component is likely to be difficult. When an AE cannot be clearly attributed to any one or combination of drugs, the most stringent criteria for dose modification (based on Dose modification for ivosidenib and ipilimumab/nivolumab - [Table \(8.12.1\) 1](#) and [Appendix 8](#)) must be used for all three drugs.

Dose delay: When study interventions are administered in combination, if the AE is considered immune-related, both nivolumab and ipilimumab interventions should be held according to recommended dose modifications ([Appendix 8](#)). QTc prolongation and other Grade3 or higher adverse events that are possibly related to ivosidenib should be managed according to dose modification recommendations in [Table \(8.12.1\) 1](#).

Re-starting Study Interventions: Subjects may not have any dose modifications (no change in dose or schedule) of nivolumab and/or ipilimumab in this study. At the 250 mg QD dose level, no dose re-escalation is allowed for ivosidenib. If the toxicity does not resolve or the criteria for resuming treatment are not met, the subject must be discontinued from all study interventions. If the toxicities do resolve and conditions are aligned with what is defined in [Appendix 8](#) and [Table \(8.12.1\) 1](#) ivosidenib, nivolumab and/or ipilimumab may be restarted at the discretion of the Investigator.

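### Protocol 8.6.1.1 makes stopping treatment optional for QTcF above 480 msec, while Table (8.12.1) 1 directs an ivosidenib hold at Grades 2 and 3

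*Protocol*

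**What the plan says.** Section 8.6.1.1 of the protocol applies to subjects on treatment whose QTcF exceeds 480 msec, that is, CTCAE Grade 2 or higher. Its first two bullets cover electrolytes and a review of QT-prolonging medication. The third applies when no alternative cause is found and the Investigator judges it appropriate, particularly if QTcF stays high after those steps. It then allows that "study treatment may be interrupted, and an ECG should be rechecked in approximately 1 week after the QT prolongation event was first observed", or more often if needed. The section closes by sending the reader to Table (8.12.1) 1 "for the management of QT prolongation by NCI CTACE grade".

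That table is titled "Management of Ivosidenib related QT Prolongation and Adverse Events by NCI CTCAE Grade". After the same electrolyte and medication review, its Grade 2 QTc row (above 480 to 500 msec) reads "Interrupt ivosidenib. Restart ivosidenib at 500 mg once daily after the QTc interval returns to less than or equal to 480 msec". Its Grade 3 row (above 500 msec) reads "Interrupt ivosidenib. Resume ivosidenib at a reduced dose of 250 mg once daily when QTc interval returns to within 30 msec of baseline", or to 480 msec or less.

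Two other places lead to the table. Section 6.1 states "For treatment dose modifications due to toxicities, please refer to Section" 8.12. Section 8.12.3, referring to the table, states "QTc prolongation and other Grade3 or higher adverse events that are possibly related to ivosidenib should be managed according to dose modification recommendations".

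**The concern.** The bullet leaves stopping to judgement and the table does not. A site that works from 8.6.1.1 has a text that lets it keep giving ivosidenib at a QTc for which the table orders a hold. Section 8.6.1, which defines QT prolongation as an event of special interest, sends sites to 8.6.1.1 for management, so the permissive bullet is likely to be read before the table.

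What is at stake is participant safety. Section 2.5 names QT prolongation as an important identified risk of ivosidenib in all subjects; the other risk it lists there is confined to hematologic malignancies. Section 4.1.3.1 reports that the risk of QT prolongation rises with ivosidenib peak concentration. A stopping instruction for that risk should read the same way wherever a site finds it.

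**Working it through.** The plan gives no figure to reproduce and no arithmetic applies. The check is whether the two texts cover the same events, whether they ask for different things, and whether any text settles the difference.

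**1. Scope.** The bullet covers every QTcF above 480 msec, without a split by grade, when no other cause is found. The table covers ivosidenib-related events, and Section 8.12.3 extends the referral to possibly related ones. Section 8.9 says that an event whose relationship to the drug cannot be ruled out is in general to be counted as related. An event with no other cause will therefore normally meet the table's condition. The scopes overlap in exactly the case that the bullet describes.

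**2. Action.**

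| QTc | 8.6.1.1, third bullet | Table (8.12.1) 1 |
|---|---|---|
| Above 480 to 500 msec (Grade 2) | Interruption of study treatment optional | Interrupt ivosidenib; restart at 500 mg once QTc is 480 msec or less |
| Above 500 msec (Grade 3) | Interruption of study treatment optional | Interrupt ivosidenib; resume at 250 mg on recovery |

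The instructions differ in both rows.

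**3. Precedence.** Section 6.1, the last line of 8.6.1.1 and Section 8.12.3 all lead to Section 8.12 or the table. None says that the table replaces or limits the bullet, and 8.12.3 calls the table's contents recommendations. Two further rules do not settle it:
- The rule in 8.12.3 that the most stringent criteria apply when attribution is unclear compares the table with Appendix 8, not with 8.6.1.1.
- The general clause in 8.12.1 lets the Investigator delay or modify ivosidenib for any adverse event. It does not say that a hold directed by the table may be omitted.

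**4. Other mandatory holds.** Section 4.1.4.3 requires all three drugs to be interrupted for a dose-limiting toxicity (DLT). Under Section 4.1.4.2 that does not reach Grade 2 QTc prolongation, or any event after Day 42 (2 cycles of 21 days).

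**5. SAP.** Section 5.4.4.2 lists ECG values and flags the maxima. It contains no management rule, so the analysis neither depends on the conflict nor resolves it.

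**The case against.** The best defence is that the section resolves itself. The bullets are general steps, and the closing line names the table as the instruction by grade. With three pointers in the same direction, a careful reader would follow the table. This stands, and it is why the point is minor.

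A second defence is that the texts can be read together. The Safety Analysis Set definition in Section 10.1.2 glosses study treatment as the three-drug combination. On that reading, holding the whole regimen is optional while the ivosidenib hold follows the table. The reading is available, but 8.6.1.1 does not state it, and study treatment includes ivosidenib. The replacement text should make the distinction explicit.

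Third, there are safeguards. QT events go to the Sponsor within 24 hours as events of special interest, and Section 8.12.1 asks that decisions to delay or modify ivosidenib be discussed with the Sponsor beforehand. Both help, but only in part. Section 8.6.1 sets the reporting threshold at Grade 2 while 8.6.1.1 says Grade 3, and a decision simply to continue dosing is not plainly a dose modification.

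Two stronger readings may tempt a reader, and the documents support neither.
- **DLT timing.** One might infer that a Grade 3 event cannot be called a DLT for 7 days, so that dosing above 500 msec could go on while its status is open. Section 4.1.4.2 makes treatment-related, non-immune events of Grade 3 or higher DLTs, with exclusions that include Grade 3 QTc prolongation resolving to Grade 1 within 7 days. It is equally open to treat the event as a DLT until resolution is shown, which triggers the immediate hold.
- **Grade 4.** One might contrast the optional bullet with the permanent stop for "Grade 4 AEs (related) including QTc interval prolongation with signs/symptoms of life-threatening arrhythmia". That row requires arrhythmia signs or symptoms. A bullet built around an ECG recheck in about a week would not plausibly displace it.

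**Conclusion.** The inconsistency is real at Grades 2 and 3: for a QTcF above 480 msec with no other cause found, one text makes interruption optional and the other directs an ivosidenib hold. It is minor, because the cross-references favour the table and the safeguards limit the chance that a site acts on the bullet alone. It should still be corrected, since it concerns a stopping instruction for an identified risk in all subjects.

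The reach is small. SAP Section 5 records that enrollment stopped after 7 patients in the Safety Lead-in, and SAP Section 1 gives an early termination letter dated 21 August 2024. Termination alone does not make the point moot: Protocol Section 4.3.1 lets subjects who benefit stay on ivosidenib if the study ends for reasons other than safety. Whether anyone did is not stated.

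A reader should not infer that any participant was dosed wrongly, since the documents report no QT events. Nor is there a consequence for any estimand, analysis or listing.

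The conclusion rests on one assumption: that an event with no other identified cause is classed as related or possibly related to ivosidenib, as Section 8.9 indicates.

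**What to change.** Replace the third bullet of Section 8.6.1.1 with:

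> If the event is related or possibly related to ivosidenib (including when no other cause has been found), interrupt or discontinue ivosidenib by grade as set out in Table (8.12.1) 1, which governs ivosidenib dosing. Interruption of nivolumab and ipilimumab is at the Investigator's discretion, subject to Section 8.12.3 and Appendix 8, unless the event is a DLT, in which case Section 4.1.4.3 applies to all three drugs. Repeat the ECG after about 1 week, or more often if clinically needed.

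The reference to Section 8.12.3 and Appendix 8 keeps the new sentence from cutting across the rule on unclear attribution. Leave the electrolyte and medication-review bullets as they are.

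The cost is one bullet in one section, issued as a clarification to sites with any participant still on ivosidenib. It needs no new data and no change to the SAP.
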